### 8.4 Study Drug Administration

RSLV-132 or placebo will be administered intravenously at 10 mg/kg at baseline, then weekly for two weeks and then once every 2 weeks for the next 20 weeks (13 administrations) to subjects with SLE. The preparation of the study drug and rate of infusion will be provided in the Study Drug Reference Manual. For each dose, the date, actual infusion rate, start and stop time of infusion will be recorded in the source documents and transcribed into the CRFs.

**8.5 Study Drug Accountability**

The unblinded pharmacist will maintain an accurate record of the receipt of the Investigational Product as shipped by the Sponsor (or designee), including the date received. In addition, an accurate drug disposition record will be kept, specifying the amount dispensed to each subject and the date of dispensation.

**8.6 Study Drug Handling and Disposal**

At the completion of the study, all unused drug supplies will be destroyed by the sites after final accountability and reconciliation with the dispensing log.

## 9 ASSESSMENT OF SAFETY

Safety of the treatment will be compared between the two groups by assessing adverse events and laboratory results as well as any physical findings that have changed from baseline.

All patients who have received any infusion with either RSLV-132 or placebo will be included in the overall analysis of safety. All data relating to safety will be listed and summarized by treatment group using descriptive statistics. The change from baseline for each of the vital signs parameters will also be computed and included in individual patient listings and descriptive summaries.

Deaths that occur during the study and the proportion of subjects discontinuing the study due to adverse events will as well be summarized by treatment group.

All adverse events will be coded and tabulated by MedDRA System Organ Class (SOC) and preferred term (PT) and presented in descending frequency. Adverse events will also be tabulated by severity and relationship to the study medication. Serious adverse events will be summarized separately.

### 9.1 Adverse Event Definition

An adverse event (AE) is any untoward medical occurrence in a subject administered a pharmaceutical product that does not necessarily have a causal relationship with this treatment. Adverse events may be reported by the subject, discovered by Investigator questioning, or detected through PE, a laboratory test requiring further attention, or other means.

Adverse events can therefore be any unfavorable or unintended sign, symptom or disease temporally associated with the use of an investigational medicinal product, whether or not considered related to the investigational medicinal product. Adverse events include:

- Any sign, medical diagnosis or symptom
- Any new undesirable medical experience or unfavorable and unintended worsening of an existing condition that occurs during or after treatment, whether or not considered related to study drug
- Abnormal laboratory results that have associated symptoms or findings, require specific treatment, or require a change in subject management.

Whenever possible, the Investigator should group signs or symptoms that constitute a single diagnosis under a single event term. For example, cough, rhinitis and sneezing might be grouped together as “upper respiratory tract infection”. If possible, abnormal laboratory results that meet the definition of an AE (that warrant management, investigation or treatment) should be reported as a clinical diagnosis rather than the abnormal value itself (e.g., “anemia” rather than “decreased blood count”). Adverse events will be graded according to the Rheumatology CTC (Woodworth et al., J. Rheumatology 2007; 34(6): 1401-1414).

## 9.2 Serious Adverse Event Definitions

An AE is classified as serious if it meets any of the following criteria:

- Results in death
- Is life-threatening
  - This definition implies that the subject, in the view of the Investigator, was at immediate risk of death at the time of the event. It does not include an event that, had it occurred in a more severe form, might have caused death.
- Requires in-patient hospitalization or prolongs an existing hospitalization
  - Hospitalizations for surgeries planned before study entry, for social reasons, or for normal disease management procedures (including treatment adjustment) are not to be considered SAEs according to this criterion.
- Results in persistent or significant disability and/or incapacity
- Results in an adverse outcome in a child or fetus of a patient exposed to the study treatment regimen before conception or during pregnancy.
- Otherwise considered medically important in the judgment of a health care professional. Medical and scientific judgment should determine whether an AE is classified as an SAE in many situations. Medically important conditions that may not result in death, not be life-threatening, nor require hospitalization, may be considered SAEs when they may jeopardize the subject or may require intervention to prevent one of the outcomes listed above. Examples of such events are allergic bronchospasm requiring intensive treatment in an emergency room, blood dyscrasias or convulsions that do not result in in-patient hospitalization.

## 9.3 Adverse Event Reporting

All AEs, both serious and non-serious, will be recorded on the AE CRF at each visit from the time the subject receives the first dose of study medication until the End of Study visit.

## 9.4 Serious Adverse Event Reporting Requirements

SAEs will be reported to Resolve on the SAE report form within 24 hours of awareness of the event by the investigator.

In the event that the investigator does not become aware of the occurrence of a SAE immediately, the investigator is to report the event within 24 hours of his/her first awareness of the SAE.

Any SAE occurring any time after the reporting period must be promptly reported if a causal relationship to investigational product is suspected.

The initial report should include as much relevant information as possible but at a minimum should include subject Number, date of event onset, event term/description of event, investigator's assessment of relationship to study drug.

For all SAEs, the investigator is obligated to pursue and provide information to Resolve or its designee in accordance with the timeframes for reporting specified above. In addition, an investigator may be requested by Resolve to obtain specific additional follow-up information in an expedited fashion. This information may be more detailed than that captured on the AE case report form. In general, this will include a description of the AE in sufficient detail to allow for a complete medical assessment of the case and independent determination of possible causality. Information on other possible causes of the event, such as concomitant medications and illnesses must be provided. All new information including final outcome should be submitted as soon as possible.

### **9.5 Non-Serious Adverse Event Reporting Requirements**

Non-serious AEs are to be reported on the AE CRFs, which are to be submitted as outlined in the study guidelines.

### **9.6 Adverse Event Follow Up**

For adverse events with a causal relationship to the investigational product, follow-up by the investigator is required until the event or its sequelae resolve, stabilize or are explained.

### **9.7 Severity Assessment**

As required on the AE case report forms, the investigator will assess the severity of an event according to the Rheumatology CTC (Woodworth et al., J. Rheumatology 2007; 34(6): 1401-1414).

### **9.8 Causality Assessment**

The investigator's assessment of causality must be provided for all AEs (serious and non-serious). Causality is determined as not related, possibly related, or definitely related according to the following definitions:

- Not related: The event can be readily attributed to other factors such as the subject's clinical state, environmental factors, or other concomitant medications or therapies administered.
- Possibly Related: Follows a reasonable temporal sequence from administration and is unlikely to be attributed to the subject's clinical state or environmental factors or other therapies administered.
- Definitely related: Clear-cut temporal association with study drug administration with improvement on cessation of study drug AND cannot be readily attributed to other factors such as the subject's clinical state, environmental factors, or other concomitant medications or therapies administered.

### **9.9 Abnormal Test Findings**

When laboratory results are outside the normal range, a decision regarding whether the result is of clinical significance or not shall be made by the Investigator and shall be based, in part, upon

the nature and degree of the observed abnormality. Abnormal evaluations may be repeated, to rule out lab error.

The criteria for determining whether an abnormal objective test finding should be reported as an AE are as follows:

- Test result is associated with accompanying symptoms, and/or;
- Test result requires additional diagnostic testing or medical/surgical intervention, and/or;
- Test result is considered to be an AE by the investigator or Sponsor.

An abnormal test result, in the absence of any of the above conditions, does not constitute an AE.

Any abnormal test result that is determined to be an error does not require reporting as an AE.

### **9.10 Hospitalization**

AEs reported from the clinical study associated with subject hospitalization or prolongation of subject hospitalization, are considered serious.

Hospitalization or prolongation of hospitalization in the absence of a precipitating, clinical AE is not an SAE. Examples include:

- Admission for treatment of a preexisting condition not associated with the development of a new AE or with a worsening of the preexisting condition (e.g., for work-up of persistent pre-treatment lab abnormality);
- Social admission (e.g., subject has no place to sleep);
- Administrative admission (e.g., for yearly physical exam);
- Protocol-specified admission during a clinical study (e.g., for a procedure required by the study protocol);
- Pre-planned or optional admission not associated with a precipitating clinical AE.

## **10 ASSESSMENT OF PHARMACOKINETICS**

### **10.1 Measurement of RSLV-132 Drug Levels**

RSLV-132 drug levels in subject serum samples will be quantitated by two different assays; a validated ELISA assay that directly measures RSLV-132 (ICON Laboratories), and a catalytic activity assay that measures the RNase enzyme activity of RSLV-132 (Resolve Therapeutics, LLC).

### **10.2 Pharmacokinetic Analysis**

Pharmacokinetic (PK) parameters will be calculated for each subject, whenever possible, based on the serum concentrations of RSLV-132.

## 11 STATISTICS

A statistical analysis plan will be prepared after completion of the final protocol and will be finalized before database lock. The statistical analysis plan will include more details on the statistical analysis and presentation of the data. The fundamentals of the analysis are listed below. Data will be analyzed and reported by subject's sex and gender.

### 11.1 Subject Population for Efficacy/Activity Analysis

The efficacy/activity analysis set will include all subjects randomized and that receive at least one dose of study drug.

### 11.2 Analysis of the Primary Objective

The primary objective is a comparison of the mean improvement (from Baseline to Day 85; or Baseline to Day 169 in CLASI Activity scores of those in the efficacy analysis set receiving RSLV-132 and those receiving placebo.

### 11.3 Analysis of the Secondary Objectives

The following secondary objectives will be compared between the two treatment arms:

- The immunogenicity of RSLV-132 as measured by the presence of RSLV-132 antibodies
- Improvements (from Baseline to Day 85 and Day 169) in the SLEDAI-2K, PGA, and BILAG-2004 scores
- Improvement (from Baseline to Day 85 and Day 169) in the FACIT-Fatigue scale
- Improvements (from Baseline to Day 85 and Day 169) in tender or swollen joint count
- Reduction in oral steroids at Day 169 relative to Day 85
- The proportion of subjects achieving a 50% improvement in CLASI activity score

### 11.4 Exploratory Analysis

Differences between the gene expression profiles, autoantibody and complement profiles, and serum protein levels will be compared between the two treatment arms. A comparison will be made of the mean improvement (from Baseline to Day 85; or Baseline to Day 169 in CLASI damage scores of those randomized to be treated with RSLV-132 and those randomized to receive placebo.

### 11.5 Subject Population for Safety Analysis

The safety of RSLV-132 will be compared between the two arms using the following safety parameters: adverse events, previous and concomitant medications, previous and concomitant diseases and laboratory data. The safety population will include all patients who received any treatment with either RSLV-132 or placebo. Randomized patients that receive the incorrect therapy from that intended will be summarized in the group according to the therapy actually received. Patients who are not randomized but who receive treatment or placebo will also be included in the safety population and summarized according to the therapy actually received. In

the unlikely event of a patient commencing one study therapy and crossing over to the other, the data for that patient will be included in summaries and analyses with the original group.

## **11.6 Sample Size**

The sample size chosen for this study was based upon precedent set by other studies of similar nature and was not based on power calculations.

## 12 STUDY PROCEDURES

### 12.1 Evaluations

Evaluations are summarized in Appendix A. During the course of the study approximately 295 mL of blood will be drawn. A central laboratory will perform all evaluations with the following exceptions:

- anti-drug antibody evaluations will be performed by ICON.
- autoantibody assessments will be performed by the University of Washington Clinical Laboratory.
- measurement of drug concentration by will be performed by ICON.
- measurement of RNase enzyme activity will be conducted by Resolve Therapeutics.
- serum protein analysis will be conducted by Myriad RBM.
- blood-cell gene expression analysis will be performed by Q Solutions.
- Each site will perform a urine pregnancy test on females at the baseline visit only

Every attempt will be made to perform evaluations on the scheduled day and time, as appropriate. If evaluations cannot be performed on the day of the scheduled visit a window of  $\pm$  3 days may be applied for visit Days 8 through 155 and  $\pm$ 5 days for Day 169 and Day 215. In the event visit windows are utilized the minimum interval between administrations of RSLV-132 should be 10 calendar days.

All scheduled study visits should occur on the specified number of days after Baseline, even if a preceding visit occurred off-schedule.

### 12.2 Screening Procedures

The following Screening procedures will be performed for all potential subjects at a visit conducted within 28 days of study entry (prior to Baseline):

- informed consent;
- assess inclusion/exclusion criteria;
- demographic data;
- weight, and height;
- viral load for hepatitis-B and C and HIV (Appendix B);
- physical examination;
- pregnancy test (serum);
- medical and medication history;
- vital signs (temperature, respiratory rate, blood pressure and pulse);
- clinical laboratory evaluations (including Chem-20, CBC, and UA), laboratory evaluations may be repeated if abnormal;
- measurement of cutaneous SLE activity (CLASI);
- photographs of cutaneous SLE lesions for adjudication (if CLASI  $\geq$ 10);
- evaluation of autoantibody profile (Ro-52/60, La, Sm, SmRNP, U1 RNP A/68) local or central laboratory.

### 12.3 Baseline (Day 1) Procedures

Prior to study drug administration (pre-dose procedures):

- the inclusion/exclusion criteria will be re-evaluated (CLASI score and concomitant medications only);
- directed physical examination;
- pregnancy test (urine);
- AE Assessment;
- interim medical/medication history;
- vital signs (temperature, respiratory rate, blood pressure and pulse);
- clinical laboratory evaluations (Chem-20, CBC, and UA);
- measurement of SLE disease activity (CLASI, SLEDAI-2K, BILAG-2004, PGA);
- tender and swollen joint count
- photographs of cutaneous SLE lesions;
- FACIT Index (subject completes form);
- serum sample for study drug concentration;
- serum for protein analysis;
- serum sample for measurement of RNase activity;
- whole blood for gene expression profile;
- serum sample for autoantibody profile (Ro-52/60, La, Sm, SmRNP, U1 RNP A/68, dsDNA) C3 and C4 (local or central laboratory);
- serum for assessment of antibodies to RSLV-132;
- **after completion of above assessments:**
  - study drug administration

### 12.4 Procedures on Days 8, 15, 43, 71, 99, 127, and 155

Prior to study drug administration (pre-dose procedures):

- adverse event assessment;
- interim medication history;
- vital signs (temperature, respiratory rate, blood pressure and pulse);
- serum for assessment of anti-RSLV-132 antibodies (Day 15 only)
- measurement of cutaneous disease activity (CLASI) – (Days 99, 127 and 155 only);
- **after completion of above assessments:**
  - study drug administration

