**Exclusion Criteria:**

The following will exclude potential subjects from the study:

1. severe, active CNS involvement at Screening;
2. severe renal involvement at Screening (urine protein/creatinine ratio of  $>200$  mg/mmol, or an estimated creatinine clearance of  $<30$  mL/min);
3. use of cyclophosphamide within 3 months of the Baseline visit;
4. use of rituximab within 6 months of the Baseline visit;
5. use of belimumab within 3 months of the Baseline visit;
6. use of background medications within 1 month of Baseline in excess of:
  - i. mycophenolate mofetil  $> 3$  g/day;
  - ii. azathioprine  $> 200$  mg/day;
  - iii. methotrexate  $> 25$  mg/week;
  - iv. hydroxychloroquine  $> 400$  mg/day;
  - v. prednisone (or equivalent)  $> 15$  mg/day;
7. use of an intravenous steroid “pulse” within 2 months of Baseline;
8. use of an intramuscular steroid injection within 1 month of Baseline;
9. change in SLE medications within 1 month of Baseline;
10. the presence of a clinically significant infection in the judgement of the Investigator within seven days prior to the receipt of the first dose of study drug;
11. positive viral load test for hepatitis B, C, or HIV at Screening;
12. participation in another clinical trial with receipt of an investigational product within 3 months or 5 half- lives, of last administration (whichever is longer) from Baseline;
13. positive pregnancy test at Screening or at Baseline;
14. female subjects currently breast feeding at Baseline;
15. inability or unwillingness to comply with protocol-specified procedures which, in the opinion of the Investigator, would make the subject unsuitable for study participation.

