**Patient reported outcomes:**

- FACIT-Fatigue patient reported fatigue index

**Evaluations by Day:**Screening Procedures

- informed consent;
- evaluation of inclusion/exclusion criteria;
- complete medical and medication history;
- demographic data;
- weight and height;
- physical examinations;
- vital signs;
- clinical laboratory evaluations (Chem-20, CBC, and UA);
- viral load tests for hepatitis B, C, and HIV;
- serum pregnancy test;
- measurement of cutaneous disease activity (CLASI);
- Photographs of cutaneous disease activity;
- autoantibody profile (Ro-52/60, La, Sm, SmRNP, U1 RNP A/68) (local or central laboratory);
- FSH (when required to confirm menopause in female subjects)

Baseline Procedures

- confirmation of inclusion/exclusion criteria;
- interim medical and medication history;
- physical examination;
- vital signs;
- adverse event baseline assessment;

- measurement of cutaneous disease activity (CLASI);
- photographs of cutaneous manifestations of lupus;
- measurement of SLE activity (SLEDAI-2K, BILAG-2004, PGA);
- tender and swollen joint count;
- patient reported outcome, FACIT fatigue index;
- serum for study drug concentration;
- clinical laboratory evaluations (Chem-20, CBC, and UA);
- whole blood for measurement of gene expression;
- serum for protein analysis;
- serum for measurement of RNase activity;
- evaluation of autoantibody profile (dsDNA, Ro-52/60, La, Sm, SmRNP, U1 RNP A/68) from local or central laboratory;
- serum for complement analysis, C3 and C4;
- assessment of antibodies to RSLV-132;
- urine pregnancy test;
- study drug administration.

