## 6 SELECTION AND WITHDRAWAL OF SUBJECTS

Subjects who meet all of the inclusion criteria and none of the exclusion criteria will be eligible to be enrolled into the study.

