### 6.3 Subject Exclusion Criteria

The following will exclude potential subjects from the study:

1. severe, active CNS involvement at Screening;

2. severe renal involvement (urine protein/creatinine ratio of >200 mg/mmol, or an estimated creatinine clearance of <30 mL/min) at Screening;
3. use of cyclophosphamide within 3 months of Baseline;
4. use of background medications within 1 month of Baseline in excess of:
  - a. mycophenolate mofetil > 3 g/day;
  - b. azathioprine > 200 mg/day;
  - c. methotrexate > 25 mg/week;
  - d. hydroxychloroquine > 400 mg/day;
  - e. prednisone (or equivalent) > 15 mg/day;
5. use of an intravenous corticosteroid “pulse” within 2 months of Baseline;
6. use of an intramuscular steroid injection within 1 month of Baseline;
7. use of rituximab within 6 months of Baseline;
8. use of belimumab within 3 months of Baseline;
9. acute infection or history of acute infection within seven days prior to Baseline;
10. positive viral load test for hepatitis B, C or HIV at Screening;
11. receipt of an investigational product within 3 months of Baseline or five half-lives (whichever is longer);
12. positive pregnancy test at Screening or at Baseline;
13. female subjects currently breast feeding at Baseline;
14. inability or unwillingness to comply with study restrictions, return for follow up appointments, or other considerations, in the opinion of the Investigator, which would make the candidate unsuitable for study participation.

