## 17 APPENDICES

### 17.1 Appendix A: Study Procedures

Study Procedures	Screen (-28 to -1)	Baseline Day 1	Day 8	Day 15	Day 29	Day 43	Day 57	Day 71	Day 85	Day 99	Day 113	Day 127	Day 141	Day 155	Day 169 (EOT)	Day 215 (EOS)
Acceptable Visit Window (days)			$\pm 3$	$\pm 5$	$\pm 5$											
Informed Consent	X															
Inclusion/exclusion	X	X a														
Demographics	X															
Weight, height	X															
Hepatitis, HIV tests	X															
Physical exam	X	X b			X b	X b										
Pregnancy tests	X c	X d														X c
AE assessment		X	X	X	X	X	X	X	X	X	X	X	X	X	X	X
Medical/medication history	X	X e	X e	X e	X e	X e	X e	X e	X e	X e	X e	X e	X e	X e	X e	X e
Vital signs	X	X	X	X	X	X	X	X	X	X	X	X	X	X	X	X
Chem-20, CBC, UA	X	X			X		X		X		X		X		X	X
SLEDAI, BILAG, PGA, joint count		X			X		X		X		X		X		X	
CLASI	X	X			X		X		X	X	X	X	X	X	X	
Photographs of cutaneous disease	X	X							X						X	

Study Procedures	Screen (-28 to -1)	Baseline Day 1	Day 8	Day 15	Day 29	Day 43	Day 57	Day 71	Day 85	Day 99	Day 113	Day 127	Day 141	Day 155	Day 169 (EOT)	Day 215 (EOS)
Acceptable Visit Window (days)			+3	+3	+3	+3	+3	+3	+3	+3	+3	+3	+3	+3	+5	+5
FACIT index		X							X						X	
Serum for study drug concentration		X			X				X						X	X
Serum for protein analysis		X							X						X	
Serum for RNase activity		X			X				X						X	X
Whole blood for gene expression		X			X				X						X	X
Serum for autoantibody, C3, C4 profile	X	X			X		X		X		X		X		X	
Serum for ADA		X		X	X				X							X
Study Drug administration		X f	X	X f												

a CLASI activity and damage score and confirm no changes in SLE medications only

b directed physical exam

c serum pregnancy test for women of childbearing potential (7.4)

d urine pregnancy test for women of childbearing potential (7.4)

e interim medical/medication history only

f RSLV-132 or placebo shall be administered according to the infusion rate and time set forth in the Study Drug Reference Manual

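### The written Day 1 eligibility re-check covers CLASI and medications only, so it omits the infection and breast-feeding exclusions that Protocol Section 6.3 ties to Baseline

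*Protocol*

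**What the plan says.** The scope of the Day 1 eligibility check is stated in several places.

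- Protocol Section 12.3, pre-dose list: "the inclusion/exclusion criteria will be re-evaluated (CLASI score and concomitant medications only".
- Protocol Appendix A, footnote a to the Baseline inclusion/exclusion entry: "CLASI activity and damage score and confirm no changes in SLE medications only". SAP Section 2.3.3, Table 1, footnote a, has the same words.
- Protocol synopsis, Baseline Procedures: "confirmation of inclusion/exclusion criteria", with no restriction.

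The governing rule is in Protocol Section 6: "Subjects who meet all of the inclusion criteria and none of the exclusion criteria will be eligible to be enrolled into the study".

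Section 6.3 then ties several non-medication exclusions to Baseline. Exclusion 9 is "acute infection or history of acute infection within seven days prior to Baseline", exclusion 11 is "receipt of an investigational product within 3 months of Baseline or five half-lives (whichever is longer", exclusion 12 is a positive pregnancy test at either Screening or Baseline, and exclusion 13 is "female subjects currently breast feeding at Baseline". The synopsis words the infection exclusion differently: it requires clinical significance and counts back from dosing ("infection in the judgement of the Investigator within seven days prior to the receipt of the first dose of study drug").

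**The concern.** Had Section 12.3 simply called for a re-check without giving its scope, Section 6 would have filled the gap. Instead, Section 12.3 and both footnotes name the items to be re-checked and close the list with the word *only*. The closed list leaves out criteria whose status is defined at Baseline and can change after Screening.

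Section 12.1 points to Appendix A as the summary of evaluations, so a site may reasonably build its Day 1 eligibility form from the schedule and its footnote. Such a form would ask about CLASI and SLE medication changes. It would not ask whether the subject had an infection in the past week or is breast feeding. At stake is whether the step meant to confirm eligibility before the first infusion verifies the criteria that the protocol sets, and whether breaches of those criteria are recorded as such.

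**Working it through.** The plan gives no figure to reproduce on this point. The check is a comparison of texts and a count of days.

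**Step 1. Which exclusions are tied to Baseline.** Section 6.3 lists 14 exclusions. Numbers 1, 2 and 10 are set at Screening and number 14 has no time anchor. That leaves 14 − 3 − 1 = 10 anchored at Baseline. Six of these (3 to 8) concern SLE treatments and steroids, and the medication part of the Section 12.3 check plausibly covers them. The other 10 − 6 = 4 are infection (9), investigational product (11), pregnancy test (12) and breast feeding (13).

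**Step 2. Can Screening settle the infection criterion?** Screening is allowed from Day −28 to Day −1. SAP Section 3.2.7 numbers the day before first dose as Day −1, so the seven days before Baseline are Day −7 to Day −1.

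- Screening on Day −28 to Day −8: 28 − 8 + 1 = 21 days. The whole seven-day window lies after Screening.
- Screening on Day −7 to Day −2: 7 − 2 + 1 = 6 days. Part of the window lies after Screening.
- Screening on Day −1: 1 day. No later day of the window remains.

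Total: 21 + 6 + 1 = 28. On 21 of the 28 permitted days Screening can say nothing about this criterion, and on 21 + 6 = 27 it cannot settle it fully. These are counts of permitted days. The documents do not give the distribution of actual Screening dates, so the counts are not shares of subjects.

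**Step 3. The four exclusions, one by one.**

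| Exclusion | In the 12.3 check? | In footnote a? | Other Day 1 pre-dose source | What is left |
|---|---|---|---|---|
| Infection (9) | No | No | Interim history of symptoms (12.8), directed examination, vital signs including temperature, blood count | Information likely to be present, but no text ties it to eligibility |
| Investigational product (11) | Arguably, as a concomitant medication | No; SLE medication changes only | Interim medication history; Screening history covers current and past medications (12.8) | Minor: new receipt between Screening and Day 1 |
| Pregnancy test (12) | No | No | Urine test in the same pre-dose list; a positive result is itself the exclusion | Wording only |
| Breast feeding (13) | No | No | None named | Clear gap |

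**Step 4. Do the scopes agree?** The synopsis has no restriction. Section 12.3 is restricted to CLASI and concomitant medications. The footnotes are narrower on medications, since they cover changes to SLE medications only. The main contrast is between the unrestricted synopsis line and the other two texts; the difference between Section 12.3 and the footnotes matters only for investigational product.

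**The case against.** The strongest reply is that Section 12.3 is a list of visit procedures and does not waive Section 6.3. Section 6 continues to bar anyone who meets an exclusion. The same Day 1 list requires an examination, vital signs, laboratory tests, an adverse event assessment, a urine pregnancy test and an interim history, and places study drug after all of them. An investigator who found an infection would have to disregard Sections 6 and 6.3 in order to dose. This stands, and it limits the point: a reader might infer that the protocol lets an excluded subject be dosed, and the documents do not support that.

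Two of the four exclusions are also weaker examples. Pregnancy is tested before dosing, so no information is missing. Earlier receipt of an investigational product should be known from the Screening medication history, which leaves only new receipt in the following days.

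A reader might also infer that infections already under way on Day 1 would inflate the adverse event comparison. SAP Section 10.1 defines treatment-emergent events by onset on or after the date of first dose, so an infection with a known start on Day −7 to Day −1 is not counted. The exceptions are narrow: onset on Day 1 itself, an unclear start date, which the SAP treats as treatment-emergent, or a worsening after dosing that is reported as a new event. They do not support attaching a shift in infection rates to this point.

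The reply does not explain why the list is closed. It supplies no link from the Day 1 infection findings to eligibility, and no procedure that asks about breast feeding.

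**Conclusion.** The contradiction is real and should be corrected. Section 12.3 and footnote a of Appendix A and SAP Table 1 restrict the Day 1 check in a way that cannot be squared with Section 6, with the Baseline-anchored exclusions of Section 6.3, or with the synopsis.

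The gaps differ in size. Infection is omitted from the written check although Screening cannot address it on 21 of 28 permitted days; the relevant assessments are done, but their use for eligibility is not stated. Breast feeding is omitted and no Day 1 procedure names it. New receipt of an investigational product is a minor gap that arises under the footnotes. Pregnancy is an inconsistency of wording.

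The conclusion rests on reading *only* in its ordinary sense and on the assumption that sites rely on the visit list and schedule when they complete the eligibility check. It does not depend on any estimate of how many subjects would be affected, which the documents do not allow.

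**What to change.** Remove *only* from Section 12.3 and from footnote a in Appendix A and in SAP Table 1. State in its place that every criterion that Section 6.3 ties to Baseline is confirmed before the first infusion: CLASI and medications as now, plus infection, investigational product, the urine pregnancy result and breast feeding. The existing pre-dose assessments supply the information, except that a breast-feeding question must be added. Bring the synopsis line and these passages to one common scope.

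The two wordings of the infection exclusion, in the synopsis and in Section 6.3, must also be reconciled so that the check refers to a single criterion. This review does not say which is right.

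The cost is wording in the protocol, the SAP table and the eligibility form, plus one question on Day 1. The downside is that a few subjects may be delayed or fail at Baseline. If enrolment is already complete, the Day 1 histories can be compared with Section 6.3 when major deviations are settled before database lock (SAP Section 6.3).
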